2.0 OBJECTIVES AND SCIENTIFIC AIMS

Aim 1: To determine the feasibility of *automated geriatric co-management program* in the care of geriatric oncology patients.

The feasibility of the program will be assessed by the percentage of patients in whom at least half of the recommendations made by the program are followed by the surgical team. Our program will be deemed **feasible** if at least 50% of recommendations are followed in at least 70% of patients with impairments.

We based our cutoff based on multiple studies. A study done on surgeons' attitude toward assessment and management of older cancer patients, Ghignone et al[1], showed that only 6.4% of surgeons use geriatric assessment in their daily practice and only 36% collaborate with geriatricians in some form. Studies on geriatric comanagement of older adults who are receiving chemotherapy also showed that the pickup rate of interventions by the medical oncologists is around 35% [2]. Given these findings, we hypothesized that a more than 50% adoption of recommendations would be a reasonable rate for then refining the intervention and conducting an R01 study in the future.

Aim 2: To compare the effect of *automated geriatric co-management* program with in-person geriatric co-management on adverse surgical events.

Aim 3: To compare the effect of automated geriatric co-management program with in-person geriatric co-management on postoperative functional recovery.

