11.0 BIOSTATISTICS

This is a prospective, randomized trial of automated geriatric co-management in patients presenting to the surgery clinic for surgery compared with standard in-person geriatric co-management. Patients will be randomized 1:1 to either arm according to section 12.2.

Primary Aims

Feasibility of the automated geriatric co-management program in the care of geriatric oncology patients.

Among patients randomized to the automated geriatric arm of the study we will calculate the proportion of patients for whom at least half of the recommendations made were followed by the surgical team. **Our program will be deemed feasible if at least 50% of recommendations are followed in at least 70% of patients with impairments.** We based our cutoff based on multiple studies. A study done on surgeons' attitude toward assessment and management of older cancer patients, Ghignone et al[1], showed that only 6.4% of surgeons use geriatric assessment in their daily practice and only 36% collaborate with geriatricians in some form. Studies on geriatric comanagement of older adults who are receiving chemotherapy also showed that the pickup rate of interventions by the medical oncologists is around 35%[2]. Given these findings, we hypothesized that a more than 50% adoption of recommendations would be a reasonable rate for then refining the intervention and conducting an R01 study in the future.

We will first report the number of patients that were randomized to the automated geriatric comanagement arm but were subsequently referred to the geriatric in-person comanagement arm and report the distribution of recommendations made for these crossover patients. We will analyze 77 patients with at least one eRFA impairment who adhere to the automated geriatric comanagement arm and are not seen by geriatrics service for preoperative evaluation (crossover). In all analyses for the primary aim, we will exclude those who do not have any baseline impairment or have crossed over to the in-person geriatric comanagement arm. An interim analysis will be conducted after 38 patients are accrued. If 50% of recommendations were followed for 21 or fewer patients, the trial will be stopped for futility. Otherwise, accrual of 77 eligible patients will be completed, after which accrual will be closed to additional patients. The

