intervention will be deemed feasible if recommendations are followed for 50 patients. Finally, we will present the distribution of number of recommendations made and followed in the automated geriatric comanagement arm.

Secondary Aims

Effect of the automated geriatric co-management program compared to the in-person geriatric co-management on adverse surgical events.

All between-group comparisons will be by modified intent-to-treat (complete case analysis), with patients analyzed according to randomization, irrespective of whether they were proceeded to automated geriatric co-management or in-person geriatric co-management. To compare, by intervention arm, the proportion of patients with a composite outcome ("adverse surgical event") of either surgical complications grade 2 or higher, or prolonged hospital length of stay, or discharge to another care facility rather than home, or 30-day readmission to the hospital. Prolonged hospital length of stay will be defined as hospital length of stay greater than 75% of the cohort who underwent the similar procedure. We will test the association between intervention arm and adverse surgical event using logistic regression with the randomization stratum as the covariate.

It is plausible that the relative value of in-person vs. automated geriatric *co-management* depends on baseline risk, for instance, it could be that average risk patients are adequately managed by the automated approach, but those at high risk require individualized care. To this end, we will use a logistic regression with adverse surgical event as the outcome, study arm as the predictor, randomization strata as the covariate, and adjust for continuous baseline risk using the MSK-FI, with restricted cubic splines with knots at the tertiles to allow for non-linearity. We will then visualize the risk in both intervention arms across baseline risk to provide an individualized estimate of benefit for a given level of baseline deficit. The MSK-FI is a frailty index defined by ten sets of comorbidities, and one component related to dependency on five activities of daily living. The former will be queried from the institutional database, and the latter is assessed using the bADL and iADL measures on the eRFA.[35]

Effect of the automated geriatric co-management program with in-person geriatric co-management on postoperative functional recovery.

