We are additionally interested in using the three components, of the patient-reported functional recovery in three categories: complete recovery (defined as all three post-operative measurement score being greater than or equal to the pre-operative measurement score), partial recovery (defined as at least one, but not all three, post-operative measurement scores being greater than or equal to the pre-operative measurement score), or no recovery (defined as none of the post-operative measurement scores being greater than or equal to the pre-operative measurement score). Similarly we will use two components of the clinician-evaluate functional recovery to define three categories: complete recovery (defined as all both post-operative measurement score being greater than or equal to within 10% of the pre-operative measurement score), partial recovery (defined as at least one, but not both, post-operative measurement scores being greater than or equal to within 10% of the pre-operative measurement score), or no recovery (defined as neither of the post-operative measurement scores being greater than or equal to within 10% of the pre-operative measurement score). We will test the association between intervention arm and degree of recovery by using ordinal regression with randomization strata as covariates.

As it is likewise plausible that the relative value of in-person vs. automated geriatric co-management depends on baseline risk, we will repeat the analysis described above, related to baseline risk, for the outcomes of patient-reported functional recovery and clinician-assessed functional recovery.

Sample size

With a null hypothesis of 55% and the alternative hypothesis of 70% of patients with recommendations followed, and a one-sided α of 5% and a power of 85%, we require 77 eligible patients to be accrued in the automated geriatric co-management arm for a two-stage Simon minimax design. We expect about 25% of patients to be excluded for the primary aim due to no impairment (5%) or crossover to the in-person

geriatric comanagement arm (20%) suggesting a total accrual close to 100 per group.

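### The primary feasibility verdict has two cut-offs, 70% of patients (54 of 77) and 50 of 77 (64.9%), so a count of 50 to 53 passes one and fails the other

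*Combined protocol and SAP*

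**What the plan says.** Section 2.0, Aim 1, calls the program feasible "if at least 50% of recommendations are followed in at least 70% of patients with impairments". Section 11.0, Primary Aims, repeats the rule in bold: "Our program will be deemed feasible if at least 50% of recommendations are followed in at least 70% of patients with impairments". In both places the next sentences justify a cut-off from published surveys and uptake rates.

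The following paragraph of Section 11.0 sets out a procedure. The primary analysis uses 77 automated-arm patients who have at least one eRFA impairment and have not crossed over to in-person co-management. On the interim look it says: "An interim analysis will be conducted after 38 patients are accrued". The trial stops for futility if 21 or fewer of those patients meet the criterion. Otherwise accrual continues to 77, and the "intervention will be deemed feasible if recommendations are followed for 50 patients".

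The Sample size paragraph of Section 11.0 gives the design: "With a null hypothesis of 55% and the alternative hypothesis of 70% of patients with recommendations followed", a one-sided 5% alpha and 85% power. From these, "we require 77 eligible patients to be accrued in the automated geriatric co-management arm for a two-stage Simon minimax design".

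**The concern.** Both sentences are worded as verdict rules, and they apply to the same 77 patients with different pass marks. The value 70% also appears as the alternative hypothesis. In a Simon design the alternative is the true rate at which power is computed. It is not the observed rate needed to pass, which is lower.

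This is the go/no-go decision for the primary aim, and the plan links it to refining the intervention and seeking a larger study. If the final count is 50 to 53, the documents support opposite conclusions, and the choice between them could be made after the data are seen. If the 70% rule is the one applied, the trial does not have the power it states.

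**Working it through.** **Inputs (all from Section 11.0; the 70% rule is also in Section 2.0)**

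- Null rate p0 = 0.55, alternative p1 = 0.70, one-sided alpha 0.05, power 0.85
- Stage 1: n1 = 38, stop if 21 or fewer successes
- Total n = 77, so stage 2 adds 77 − 38 = 39 patients
- Rule A: observed proportion at least 70%
- Rule B: 50 patients, read as 50 or more

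A success is a patient for whom at least half of the recommendations were followed.

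**Step 1. Put both rules on one scale**

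- Rule A: 0.70 × 77 = 53.9. Since 53/77 = 68.8% and 54/77 = 70.1%, it needs 54.
- Rule B: 50/77 = 64.9%.
- Disputed counts: 50, 51, 52 and 53.

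**Step 2. Reproduce the plan's design**

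An exact search over two-stage designs with these error rates finds none that qualifies for n from 60 to 76. At n = 77, the qualifying design with the smallest expected size under the null stops at 21 or fewer of 38 and declares success above 49 of 77, that is, at 50 or more. The probability of early stopping at p = 0.55 is 0.575, so the expected size is 38 + (1 − 0.575) × 39 = 54.6. The plan's 77, 38, 21 and 50 are all reproduced.

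**Step 3. Error rates for each cut-off**

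For a final cut-off c and true rate p, with X1 ~ Bin(38, p) and X2 ~ Bin(39, p):

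P(feasible | p) = Σ over x = 22 to 38 of P(X1 = x) × P(X2 ≥ c − x)

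| Cut-off c of 77 | Observed rate | Type I error (p = 0.55) | Power (p = 0.70) |
|---|---|---|---|
| 49 | 63.6% | 0.0737 | 0.8936 |
| **50 (Rule B)** | 64.9% | **0.0477** | **0.8523** |
| 51 | 66.2% | 0.0292 | 0.7960 |
| 52 | 67.5% | 0.0169 | 0.7246 |
| 53 | 68.8% | 0.0092 | 0.6397 |
| **54 (Rule A)** | 70.1% | **0.0047** | **0.5454** |

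With this interim look and n = 77, a cut-off of 50 is the only one that meets both targets: 49 exceeds 5% alpha, and 51 falls below 85% power. Under Rule A, a program whose true rate is 70% would be called not feasible with probability 1 − 0.5454 = 0.455.

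The interim look does not drive this result. Without it, a cut-off of 50 gives 0.0497 and 0.863, and 54 gives 0.0048 and 0.546.

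**Step 4. Chance of a contradictory result**

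The probability of passing the interim and finishing at 50 to 53 is P(feasible | c = 50) − P(feasible | c = 54). At p = 0.70 this is 0.8523 − 0.5454 = 0.307.

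| True rate | 55% | 60% | 65% | 70% | 75% |
|---|---|---|---|---|---|
| P(50 to 53) | 4.3% | 17.2% | 33.9% | 30.7% | 11.2% |

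**The case against.** The best reply is that the governing rule can be recovered. Section 11.0 gives a full procedure with numeric bounds, and the stated design inputs return exactly those bounds. A statistician would follow the procedure and read 70% as the target rate. A pre-specified boundary therefore exists, and a choice after the fact is possible rather than certain. That is fair, but no sentence gives the procedure precedence. The 70% rule is the one in bold, it appears in two sections, it is the only rule in the aims, and it is followed by a justification of the cut-off. It also comes directly after the plan says the proportion will be calculated, so it reads as an observed rate.

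A second reply is that 70% may have been a deliberate pass mark. The documents do not settle this. The cited studies are used to support the 50% adoption figure, and nothing shows where 70% came from. The finding is therefore a conflict between two rules, not proof that one was a slip. Neither figure is miscalculated.

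A third point is the denominator. The 70% sentence refers to patients with impairments, whereas the 77 also leave out crossovers. Section 11.0 applies both exclusions to every primary-aim analysis, so using 77 for both rules is well supported, though it remains a reading.

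Finally, this is a pilot, and the observed proportion can be reported under either rule. That limits the harm, but the feasibility verdict is the primary aim, and a disputed count is a likely result.

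**Conclusion.** The concern holds. The plan states two incompatible pass marks for its primary aim, four patients apart (50 and 54 of 77). Only 50 of 77 delivers the claimed alpha and power. Using 54 cuts power at a true rate of 70% from 85.2% to 54.5% and type I error from 4.8% to 0.5%. If the true rate lies between 65% and 70%, roughly three trials in ten would end with a count on which the two rules disagree.

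This rests on two readings: that the 50-patient rule means 50 or more, as is usual for a Simon boundary, and that the 70% is taken over the 77 analysed patients. The sample size itself is correct and needs no change.

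**What to change.** Put one rule in Section 2.0 and in Section 11.0, Primary Aims. Suggested text:

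> Feasibility is declared if at least 50 of the 77 evaluable automated-arm patients (64.9%) had at least half of their recommendations followed. The 70% figure is the rate assumed under the alternative hypothesis and is not an observed pass mark.

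This also settles that 50 means 50 or more, and it names the denominator. The cost is wording in two sections, with no extra patients and no change to the interim rule. The small drawback is that readers will see that feasibility can be declared at an observed rate of about 65%.

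If the investigators do want an observed 70%, state the rule as 54 of 77 in both sections and give its operating characteristics: type I error about 0.5% and power about 55% at a true rate of 70%. More patients would not repair that power, because a pass mark equal to the assumed true rate is met only about half the time at any sample size. Higher power would have to be claimed at a true rate above 70%. Whichever rule is kept, it should be fixed before the final count is known.

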Following completion of the eRFA, the summary of impairments as well as the recommendations generated by the study team (hard-copy or email) will be provided in real-time to the thoracic surgery team for their attention. A sample is provided below. In this case, patient has impairments in various domains that ranges from KPS to number of medications.

[eRFA Summary](#)

Global recommendation: If 3 or more impairments are listed in the summary below, consider referral to geriatrics.
T = Threshold | **P** = Percentile | **PS** = Patient Score

KPS  More Information:	T: ≤ 80	P: 37%	PS: 60.
ADL  More Information:	T: < 14	P: 52%	PS: 12.
iADL  More Information:	T: < 16	P: 45%	PS: 13.
Timed Up and Go Test  More Information:	T: ≥ 10 seconds	P: 36%	PS: 10-19 seconds.
Social Support  More Information:	T: ≤ 16	P: 43%	PS: 16.
Limited Social Activity  More Information:	T: ≥ 8	P: 50%	PS: 12.
Weight Change  More Information:	T: 10 pound loss or more	P: 16%	PS: 10-20.
Distress Level  More Information:	T: ≥ 4	P: 55%	PS: 7.
Number of Medications  More Information:	T: ≥ 5	P: 45%	PS: More than ten.

Subsequently, the research staff member clicks on various impairments and would be able to view and print the recommendations for each impairment. For example, the following are the recommendations for a Timed Up and Go test impairment.

Timed Up and Go Test **T:** ≥ 10 seconds **P:** 36% **PS:** 10-19 seconds.

[More Information:](#)

[Pre/Postop Recommendation:](#)

- A- Consider consultation with physical therapy and occupational therapists.
- B- Encourage use of appropriate assistive devices.
- C- Encourage resistance exercises such as repeated chair stand in the preoperative period.
- D- Consider use of stationary bike or bike pedals in the preoperative period.

[Medical Recommendation:](#)

[Education:](#)

[Supportive Services:](#)

A copy of the recommendations will be available in EMR. After preoperative clearance by patients' primary care providers, general internal medicine service, or other services such as cardiology, patients will undergo surgery. The geriatrics service will see patients before or after surgery if the consult is requested by the surgery service. The automated co-management program is not expected to lengthen the patients' first visits.

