7.1 ASSESSMENT/EVALUATION PLAN

Assessment and Measurement Instruments:

In this study, the data will be collected using the following instruments and measurements methods:

- Electronic Medical Record review:

- 1- For patients in the intervention group (automated geriatric co-management), we will assess the percentage of recommendations that were followed by the surgery team. For example, if automated geriatric co-management recommends consultation with physical therapy perioperatively, we will assess whether the consult has been obtained.
- 2- For patients in both groups, we will assess the adverse surgical events by day 30 following surgery. Adverse surgical event is a composite of surgical complications grade 2 or higher, mortality after surgery, or discharge to any place other than home, or prolonged length of stay (defined as length of stay longer than 75% of the cohort who underwent the same surgical procedure), or readmission to the hospital within 30 days from surgery.

MSKCC's secondary surgical events database in the EMR has been shown to accurately record major postoperative complications within the 30 days after surgery[34].

- 3- to assess sociodemographic characteristics (age, gender, ethnicity),
- 4- to assess routine preoperative blood work (complete blood cell counts, chemistry panel).
- 5- To assess cancer characteristics (stage, receipt and type of neoadjuvant treatment)

- 6-** To assess surgical characteristics (type of surgery: minimally invasive vs open, duration of surgery, intraoperative blood loss, and American Society of Anesthesiologist Physical Status classification)
- **Four Meter Walk Test:** In order to assess functional recovery, the 4-meter walk test will be performed. In the 4-meter walk test, the time that it takes patients to walk 4 meters in their usual pace will be recorded in seconds by the clinical research staff. (This portion will be skipped for patients being seen via telemedicine.)

Assessment and Evaluation Plan

Patients will be screened for study eligibility at the time of attending their surgery appointment at MSKCC for consideration of surgery. The inclusion and exclusion criteria will be reviewed by the clinical research staff firstly to confirm the patients' eligibility status. Once eligibility has been determined and informed consent has been obtained, patients will undergo baseline assessments and subsequently randomization will occur.

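### Crossover is defined by preoperative geriatrics visits only, so automated-arm patients seen by geriatrics after surgery stay in the primary analysis, where care prompted by a geriatrician can be scored as surgical-team uptake

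*Combined protocol and SAP*

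**What the plan says.** Section 2.0 measures feasibility by whether at least half of the "recommendations made by the program are followed by the surgical team". Section 11.0 repeats this as the proportion of patients for whom "at least half of the recommendations made were followed by the surgical team".

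The analysed patients are those with at least one impairment "who adhere to the automated geriatric comanagement arm and are not seen by geriatrics service for preoperative evaluation (crossover"). Section 11.0 uses two further phrases for crossover: patients who "or have crossed over to the in-person geriatric comanagement arm" are excluded, and the number "subsequently referred to the geriatric in-person comanagement arm" is to be reported. Neither phrase has its own definition.

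Sections 4.2 and 4.3 describe the automated arm. In it, "The geriatrics service will see patients before or after surgery if the consult is requested by the surgery service". The printout given to the surgical team also carries this line: "Global recommendation: If 3 or more impairments are listed in the summary below, consider referral to geriatrics".

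Section 7.1 takes uptake from review of the electronic record. Its example is a recommended physical therapy consultation: "we will assess whether the consult has been obtained". The table in Section 9.0 places the number of recommendations followed at the 30-day follow-up.

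**The concern.** The two descriptions of geriatrics contact do not match. The automated arm permits it before or after surgery, but the crossover definition removes only the preoperative kind. A patient whom geriatrics first sees on the ward still meets the stated definition of an evaluable patient. The record check asks whether an action took place and does not ask who prompted it.

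Such contact is foreseeable. The printout suggests referral at three or more impairments, and Section 12.3 anticipates a median of four, so at least about half of randomised patients would be expected to trigger that line. The documents do not say how often a postoperative visit would follow.

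The program is justified in Section 3.1 by the shortage of geriatricians and is aimed at institutions with few or none. If some of the measured uptake depends on a geriatrician, the feasibility verdict says less about those settings. The verdict also bears on whether a larger study is pursued.

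**Working it through.** **1. Which geriatrics contact is covered**

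| Geriatrics contact in the automated arm | Allowed (4.2, 4.3) | Removed from primary set (11.0, stated definition) |
|---|---|---|
| Preoperative evaluation | Yes, on request | Yes |
| Postoperative visit only | Yes, on request | No |

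Nothing in Sections 7.1, 9.0 or 11.0 separates actions by who prompted them.

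**2. The plan's own design figure**

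Inputs from Section 11.0: null 55%, alternative 70%, one-sided alpha 5%, power 85%, 38 patients at stage 1, stop at 21 or fewer, 77 in total, feasible at 50.

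P(feasible | p) = Σ over x = 22 to 38 of Bin(x; 38, p) × P[Bin(39, p) ≥ 50 − x]

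- At p = 0.55: 0.048.
- At p = 0.70: 0.852.
- An exact search for the Simon minimax design returns 77 patients with these same bounds.

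The sample size is sound. The issue is what counts as a success.

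**3. Effect of postoperative consults on the verdict**

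The documents supply neither input, so both are assumed and varied. Let s be the share of analysed patients seen by geriatrics only after surgery, and g the probability that such a patient is scored as reaching the 50% threshold. True surgical-team uptake is set at the null of 55%. The apparent rate is

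p = 0.55 × (1 − s) + g × s

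For example, s = 0.10 and g = 0.90 give p = 0.495 + 0.090 = 0.585. Putting p into the formula in step 2 gives the chance of a feasible verdict:

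| s | g = 0.70 | g = 0.80 | g = 0.90 | g = 1.00 |
|---|---|---|---|---|
| 5% | 6.2% | 7.4% | 8.7% | 10.1% |
| 10% | 8.0% | 10.9% | 14.6% | 19.0% |
| 15% | 10.1% | 15.6% | 22.8% | 31.7% |
| 20% | 12.7% | 21.5% | 33.3% | 47.2% |

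The reference value without such consults is 4.8%. It also applies if consults leave the success rate unchanged (g = 0.55).

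**The case against.** **The endpoint wording already limits credit to the surgical team.** Sections 2.0, 7.1 and 11.0 all say so, and a careful abstractor might refuse credit for geriatrician-led actions. A reader might infer that such actions are certain to be counted. The documents do not say that. What stands is that no attribution rule exists, so they can be counted.

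**A requested consult may itself be uptake.** Geriatrics sees these patients only when the surgical team asks, and the printout suggests referral. This is fair for the referral item. It does not extend to other recommendations that the geriatrician then prompts, and the plan excludes patients seen preoperatively rather than crediting the request.

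**The preoperative line has a design reason.** In Section 4.2 the comparator begins with a preoperative geriatric evaluation, so using that visit to mark crossover is coherent. The broader phrases about adherence and crossing over might also be read to remove a patient who was fully co-managed after surgery. But they are undefined, and a requested postoperative visit belongs to the automated arm as described. Nor do the documents say that such a visit amounts to full ward co-management.

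**A postoperative visit cannot deliver everything.** Two of the four sample Timed Up and Go recommendations are confined to the period before surgery. This argues against assuming that every consulted patient succeeds, and it stands.

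**Conclusion.** The gap holds as one of definition and attribution. The stated crossover rule leaves patients seen by geriatrics only after surgery in the primary set, and the record review has no means of separating their geriatrician-prompted actions from surgical-team uptake. Where this has an effect, it pushes the result toward feasible.

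The size cannot be fixed from the documents. With 5% to 20% of analysed patients consulted, the false-feasible chance is 6–13% at 70% success and 9–33% at 90%, against 4.8% under the plan. A reader might take 10–47% as the expected inflation. That range needs every consulted patient to reach the threshold, so it is an upper extreme. All these figures assume independent patients, the same consult share in both stages, and a surgical-team rate of 55% with or without a consult.

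This does not show that a feasible verdict would be wrong. It shows that the plan as written could not tell whether the verdict depended on geriatricians.

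**What to change.** In Section 11.0, under Primary Aims:

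1. Report the number of automated-arm patients seen by the geriatrics service after surgery, beside the crossover count already planned.
2. Prespecify a sensitivity analysis of the primary endpoint that treats any geriatrics-service visit up to day 30, pre- or postoperative, as crossover. State the feasible verdict alongside its result. Give that result as a proportion with a confidence interval, because the count of 50 belongs to a denominator of 77.

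A reader might prefer to count only actions recorded before any geriatrics consult. That would discard genuine surgical-team actions that happen to come later. It would also need a time for every recommendation, including items phrased as encouragement that may leave no order in the record.

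The cost is SAP wording and the geriatrics visit dates, from a record already under review. The sensitivity set is smaller: with 20% removed, 77 × 0.80 ≈ 62 patients remain. At an uptake of 70%, the 95% half-width 1.96 × √(0.70 × 0.30 / n) then widens from about 10.2 to 11.4 percentage points. Uptake may come out slightly lower. Because the set is selected on a postoperative event, it should support the primary analysis and not replace it.
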